4.1 Inclusion and Exclusion Criteria

4.1.1 Inclusion Criteria

- 101 Subject has provided informed consent prior to initiation of any study-specific activities/procedures
- 102 Male or female age \geq 18 years at the time of informed consent
- 103 Histologically confirmed diagnosis of melanoma
- 104 Subject with stage IIIB to IVM1c melanoma for whom surgery is not recommended
- 105 Subject who is treatment naïve **or had received prior treatment** for melanoma. **Any systemic treatment for melanoma must have been completed at least 28 days prior to enrollment**

- 106 Candidate for intralesional therapy (ie, disease is appropriate for direct injection or through the use of ultrasound guidance) defined as one of the following:
- at least 1 injectable cutaneous, subcutaneous, or nodal melanoma lesion ≥ 10 mm in longest diameter, or
 - multiple injectable melanoma lesions that in aggregate have a longest diameter of ≥ 10 mm
- 107 Measurable disease defined as one or more of the following:
- at least 1 melanoma lesion that can be accurately and serially measured in at least 2 dimensions and for which the greatest diameter is ≥ 10 mm as measured by contrast-enhanced or spiral computed tomography (CT) scan, magnetic resonance imaging (MRI), or ultrasound for nodal/soft tissue disease (including lymph nodes)
 - at least 1 ≥ 10 mm superficial cutaneous or subcutaneous melanoma lesion as measured by calipers
 - multiple superficial melanoma lesions which in aggregate have a total diameter of ≥ 10 mm
- 108 Serum lactate dehydrogenase (LDH) levels ≤ 1.5 X upper limit of normal (ULN) within 28 days prior to enrollment
- 109 Eastern Cooperative Oncology Group (ECOG) performance status of 0 or 1 (see [Appendix E](#))
- 110 Adequate organ function determined within 28 days prior to enrollment, defined as follows:
- absolute neutrophil count $\geq 1500/\text{mm}^3$
 - platelet count $\geq 75,000/\text{mm}^3$
 - hemoglobin ≥ 8 g/dL without need for hematopoietic growth factor or transfusion support
 - serum creatinine ≤ 1.5 x ULN
 - serum bilirubin ≤ 1.5 x ULN
 - aspartate amino transferase (AST) ≤ 2.5 x ULN
 - alanine amino transferase (ALT) ≤ 2.5 x ULN
 - alkaline phosphatase ≤ 2.5 x ULN
 - serum albumin ≥ 2.5 g/dL
 - prothrombin time (PT) ≤ 1.5 x ULN (or international normalization ratio [INR] ≤ 1.3)*
 - partial thromboplastin time (PTT) ≤ 1.5 x ULN*

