The recommended volume of talimogene laherparepvec to be injected into the tumor(s) is dependent on the size of the tumor(s) and should be determined according to the injection volume guideline in [Table 1](#). The tumor size assessment should be done by clinical exam using ruler or caliper for cutaneous and palpable and protruding subcutaneous and nodal lesions, or by measurements under ultrasound of deep-seated subcutaneous and nodal lesions.

Table 1. Talimogene Laherparepvec Injection Volume Guideline Based on Tumor Size

Tumor Size (longest dimension)	Maximum Injection Volume
> 5.0 cm	4.0 mL
> 2.5 cm to 5.0 cm	2.0 mL
> 1.5 cm to 2.5 cm	1.0 mL
> 0.5 cm to 1.5 cm	0.5 mL
≤ 0.5 cm	0.1 mL

At baseline, if there are ≥ 2 lesions, one **cutaneous, subcutaneous or nodal** lesion (ie, the lesion considered lowest priority for injection) should be left uninjected at least until it is biopsied at week 6 (see [Section 7.2.2](#)). **(No biopsy will be taken at week 6 for subjects with 1 lesion present at baseline)**. All other reasonably injectable lesions (cutaneous, subcutaneous, and nodal disease that can be injected with or without ultrasound guidance) should be injected with the maximum dosing volume available on an individual dosing occasion ([Table 1](#)). On each treatment day, prioritization of injections is recommended as follows (aside from leaving one lesion uninjected until it is biopsied at week 6):

- any new injectable tumor that has appeared since the last injection
- by tumor size, beginning with the largest tumor
- any previously uninjectable tumor(s) that is now injectable, including the previously uninjected lesion(s) after the biopsy at week 6 if now injectable

It is recommended that each lesion should receive the maximum amount possible to inject due to tumor properties at each visit before moving on to the next lesion, using the prioritization model above and the injection volume guideline based on tumor size per [Table 1](#). Lesions should be injected until the maximum volume per day (4.0 mL) has been reached or there are no further injectable lesions, whichever comes first.

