- ^p Tumor biopsy **from cutaneous, subcutaneous or nodal lesions** for biomarker analysis **should not be collected prior to the subject being enrolled. Tumor biopsy should be collected** (within 5 days prior to **first** talimogene laherparepvec administration) from one lesion at day 1 of week 1 [**Cycle 1**] and, if there are ≥ 2 lesions at baseline and one is left uninjected as described in [Section 6.2.1.1](#), from an uninjected lesion **within 7 days prior to dose** at day 1 of week 6 [**Cycle 3**]. Also **within 7 days after documentation of disease progression followed by treatment discontinuation** from the **available cutaneous, subcutaneous or nodal** lesion responsible for PD **and easily accessible for biopsy with or without ultrasound guidance**. Note: uninjected lesion biopsied at day 1 of week 6 [**Cycle 3**] must be different lesion from the lesion biopsied at day 1 of week 1 [**Cycle 1**].
- ^q Investigator's clinical measurement of cutaneous, subcutaneous, or nodal tumor by caliper at screening, day 1 of week 12 (± 1 week) [**Cycle 6**] and then every 12 weeks (± 1 week), or more frequently if clinically indicated, until clinically relevant disease progression beyond 6 months of treatment (per modified WHO response criteria, [Appendix D](#)) or until the start of a new anticancer therapy. The screening measurement must be done within 28 days prior to enrollment and will be used as baseline. If subject discontinues talimogene laherparepvec for reason other than disease progression or death, clinical tumor measurements are to be performed at safety follow-up visit (if not performed within previous 4 weeks [+ 1 week]) and every 12 weeks (± 1 week) during the long term follow-up period until clinically relevant disease progression beyond 6 months of treatment (per modified WHO response criteria, [Appendix D](#)) or until the start of a new anticancer therapy.

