- **Splitting lesions:** When an index or new measurable lesion splits into two or more lesions the largest measurable part of the split lesion should be considered to be the previously recorded index or new measurable lesion with measurements provided for the current assessment with the comment indicating that the lesion split from the specified lesion, and followed for future assessments. The remaining lesions would be reported as a new measurable lesions or new non-measurable lesions depending on measurability with a comment indicating that the lesion split from the specified lesion. In this case, appearance of a new lesion from a previous lesion will not be considered a disease progression solely due to appearance of a new lesion (may be considered a disease progression due to > 25% increase in the sum of the products of the perpendicular diameters of all index tumors since baseline, or the unequivocal appearance of a new tumor, other than the product of the split tumor, since the last response assessment time point).

Measurable Tumor Assessment/Burden:

Baseline Documentation of “Index Lesions”:

All baseline evaluations should be performed as close as possible to enrollment and never more than 4 weeks (ie, 28 days) prior to enrollment.

At baseline, up to 10 measurable cutaneous, nodal, or soft tissue lesions will be chosen to measure over the course of therapy. The distribution of these index lesions should be representative of the subject's overall disease status. Index lesions should be selected on the basis of their size (lesions with longest bi-dimensionally perpendicular diameters) and suitability for accurate repeated measurements by imaging techniques (CT, MRI or ultrasound) and/or other method such as clinical exam.

The sum of the products of the two largest of perpendicular diameters (SPD) of all index lesions will be calculated and reported.

If subject has multiple small superficial melanoma lesions at baseline (less than 10 mm in longest diameter) which in aggregate have a total diameter of ≥ 10 mm, up to 10 largest lesions that were included in this measurement will be reported as "Index Lesions", and sum of the products of the two largest of perpendicular SPD of these lesions will be calculated and reported for tumor response assessments.

Baseline Documentation of "Nonindex Lesions":

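### Biopsied lesions can serve as index lesions against a pre-biopsy baseline, so shrinkage caused by a protocol biopsy counts towards partial response

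*Protocol*

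**What the plan says.** **Who is eligible.** Inclusion criterion 107 (Protocol 4.1.1) accepts a single lesion of at least 10 mm, or "multiple superficial melanoma lesions which in aggregate have a total diameter of ≥ 10 mm".

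**Which lesions are index lesions.** Appendix D allows up to 10, chosen for size and for suitability for repeated measurement. On the small-lesion route, "up to 10 largest lesions that were included in this measurement will be reported as" index lesions. Appendix D has rules for merging, splitting and previously treated lesions, but none for a lesion biopsied under the protocol.

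**What the baseline is.** Table 2, footnote q, on caliper measurement: "The screening measurement must be done within 28 days prior to enrollment and will be used as baseline". Footnote r says the same of imaging. Appendix D (definitions of measurable and nonmeasurable) and SAP Section 6 put it differently: baseline is the latest assessment or value up to the first dose.

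**When biopsies happen.** Under Table 2, footnote p, biopsy tissue "should not be collected prior to the subject being enrolled". It is then taken "from one lesion at day 1 of week 1". With two or more lesions, an uninjected lesion is biopsied at week 6 and "must be different lesion from the lesion biopsied at day 1 of week 1". A single-lesion subject is spared only the second biopsy (Section 6.2.1.1): "No biopsy will be taken at week 6 for subjects with 1 lesion present at baseline". Biopsies come from cutaneous, subcutaneous or nodal lesions (Section 7.2.2), and index lesions are drawn from the same kinds of disease.

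**How response is scored.** The first scheduled response assessment is week 12. Partial response (PR) is a fall in SPD of 50% or more from baseline, and Appendix D does not require confirmation.

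**The concern.** The baseline is read before the first biopsy, both biopsies come before the first response assessment, and nothing keeps the sampled lesions out of the index set. Tissue lost to biopsy is then indistinguishable from tissue lost to treatment. A single-lesion subject has no other lesion to use. A subject with a few small lesions has little choice either, because the largest ones become index lesions.

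At stake are ORR, which is half of the primary CD8+ correlation, and the planned Pearson correlation between CD8+ change and the largest fall in index lesions. Exposure is systematic. Section 10.2 assumes that 100 of 110 subjects have an evaluable baseline density and that 55 have evaluable biopsies both before and on treatment. Every subject in the biomarker evaluable set needs a baseline and a week 6 value, so each has had two lesions sampled.

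**Working it through.** **1. The plan's own figure.** Section 10.2 gives 88% power for a one-sided 5% Fisher's exact test, with ORR 13.2% versus 39.6% and 100 evaluable subjects split at the median. Exact enumeration over two binomials of 50 gives 88.4%, so the figure is reproduced. The issue is how response is measured, not that calculation.

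**2. Order of events.** Screening measurement (baseline), then enrolment, day 1 biopsy, first dose, week 6 biopsy of a different lesion, and week 12 assessment. Table 2 schedules no formal two-diameter re-measurement between baseline and week 12.

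**3. Effect on SPD.** Fall = 1 − (SPD after biopsy ÷ baseline SPD). The documents do not give the tissue removed, so the sizes below are assumptions, with no other change in the tumour.

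Single lesion, partly removed:

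| Baseline | 4 mm off one diameter | 4 mm off both |
|---|---|---|
| 10 x 10 mm | 1 − 60/100 = 40% | 1 − 36/100 = 64% (meets PR) |
| 20 x 20 mm | 1 − 320/400 = 20% | 1 − 256/400 = 36% |
| 30 x 30 mm | 1 − 780/900 = 13% | 1 − 676/900 = 25% |

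A biopsy that leaves both diameters as they were gives 0%.

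Equal small lesions, if a lesion is removed whole and if its remaining contribution is scored as zero (the documents do not say that it is):

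| Index lesions | Aggregate diameter | One removed | Two removed |
|---|---|---|---|
| Two, 5 x 5 mm | 10 mm | 25/50 = 50% | – |
| Three, 4 x 4 mm | 12 mm | 16/48 = 33% | 32/48 = 67% |
| Four, 4 x 4 mm | 16 mm | 16/64 = 25% | 32/64 = 50% |
| Five, 2 x 2 mm | 10 mm | 4/20 = 20% | 8/20 = 40% |
| Ten, 3 x 3 mm | 30 mm | 9/90 = 10% | 18/90 = 20% |

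The effect can reach the PR threshold with one lesion near 10 mm or with about four small lesions or fewer. It is small in bulky or numerous disease.

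**4. Pure illustration, not an estimate.** Let f be the share of true non-responders scored as PR because of biopsy. An observed rate is p + f(1 − p).
- f = 5%: low 0.132 + 0.05 × 0.868 = 17.5%; high 0.396 + 0.05 × 0.604 = 42.6%; ORR 30.1%; power 82.4%.
- f = 10%: low 21.9%; high 45.6%; ORR 33.8%; power 76.1%.

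No value of f can be drawn from the documents. These lines show only the direction if misclassification is unrelated to CD8+ density: ORR rises and the contrast shrinks.

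**The case against.** The strongest case is that this is a missing clarification rather than a demonstrated bias. Much of it stands.

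- **Zero scoring is not prescribed.** A reader might infer that a lesion taken out by biopsy is entered as 0 x 0. Appendix D gives that instruction only for coalesced lesions. A removed index lesion could equally be called unable to evaluate (Table 5), which under Table 7 gives an overall UE unless non-index disease has progressed. It could also be handled like a resection under Section 6.5, where the response of the other lesions decides. The documents do not choose, so sites could score the same event differently.
- **Whole removal is often implausible.** Section 6.2.1.1 contemplates injecting the week 6 lesion after its biopsy. With two lesions, one is held back until week 6, so removing the other whole on day 1 would leave nothing to inject.
- **Lesions are measured between visits.** Section 6.2.1.1 sizes lesions by ruler, caliper or ultrasound to set injection volume. That reading uses the longest dimension only, is not the SPD assessment, and is not designated as baseline.
- **The baseline wording could help.** The Appendix D and SAP definitions would admit a post-biopsy, pre-dose reading. None is scheduled, footnotes q and r point to screening, and no pre-dose reading can cover week 6.
- **Several examples sit exactly on 50%.** Any growth in the remaining tumour would undo those PRs, and new lesions or non-index progression can block PR. The week 6 lesion has the lowest injection priority, so it is probably among the smaller ones.
- **Investigators have some discretion.** The phrase limiting index lesions to a maximum of 10, and the measurability criterion, let them avoid a biopsied lesion when others exist. A single-lesion subject offers no such choice.

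All analyses are described as descriptive, and parts of the SAP are redacted, so its silence proves nothing. None of this supplies a rule for a partly biopsied index lesion, whose reduced diameters enter the SPD as they stand.

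**Conclusion.** The gap is documented: under the stated rules, any fall in an index lesion's diameters caused by the day 1 or week 6 biopsy counts towards PR. It matters mainly for a single lesion near 10 mm or a few lesions under 10 mm, little for bulky disease, and not at all where the biopsy leaves the diameters unchanged.

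Its frequency cannot be determined. Section 7.3.2 leaves biopsy technique to the Laboratory Manual, and the documents give no share of subjects with low-volume disease. A reader might infer that ORR is inflated, or power eroded, by a stated number of points; the documents do not support that, and the figures in step 4 of the working are illustration only. A reader might also infer that the durable response rate is inflated. That would need the artefact to persist through later assessments, which has not been shown.

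This is a cheap improvement to endpoint definition that removes an avoidable source of bias. It is not evidence that the planned ORR or the 88% power figure is wrong.

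**What to change.** Amend Appendix D as follows.

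1. Do not choose a lesion intended for the day 1 or week 6 biopsy as an index lesion when another suitable lesion exists.
2. Where this is unavoidable, record a two-diameter caliper measurement after the day 1 biopsy and before the first dose, and use it as that lesion's baseline. This agrees with the baseline definitions in Appendix D and SAP Section 6. Reconcile Table 2 footnotes q and r with that wording. If an index lesion is biopsied at week 6, measure it before and after and compare SPD on the same basis, for example by scaling its baseline contribution by the after-to-before ratio.
3. Leave an index lesion wholly removed by a protocol biopsy out of both the baseline and the follow-up SPD, and state what happens if no index lesion then remains.
4. In the SAP, report ORR excluding biopsied lesions as a sensitivity analysis, with a stated rule for single-lesion subjects. Record biopsy type and lesion identifier so that this can be done.

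The cost is Appendix D and SAP wording, plus caliper readings at visits that already take place. The downside is slightly fewer index lesions, or a smaller baseline SPD, in subjects with few lesions.

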2.3 Rationale

The purpose of the study is to explore the correlation between baseline intratumoral CD8+ cell density and objective response rate (ORR) in subjects with unresected stage IIIB to IVM1c melanoma. In addition, the study is planned to inform on the mechanism (s) of systemic action of talimogene laherparepvec on distant metastatic tumors and to identify candidate biomarkers which may predict treatment outcome. Biopsy samples will be used to investigate the relationship between intratumoral CD8+ cell density and response to treatment. Leaving one lesion uninjected during the treatment for biopsy at week 6 is critical for defining the proposed locally-initiated systemic anti-tumor immune response of talimogene laherparepvec. One hypothesis is that tumors with significant number of infiltrating CD8+ T cells will be more likely to respond to an immunotherapy with talimogene laherparepvec. Additionally, we hypothesize that talimogene laherparepvec treatment increases the number of tumor antigen specific T cells and further that subjects with higher levels of tumor antigen specific T cells will have greater response to treatment. In addition to examining the association, if any, between tumor infiltrating T cells prior to treatment and clinical response to treatment, a number of other biomarkers will be assessed to determine any association with response. CCI [REDACTED]

[REDACTED]

[REDACTED]

[REDACTED]

[REDACTED]

[REDACTED]

[REDACTED]

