A subject will be treated with talimogene laherparepvec until the subject has achieved a CR, all injectable tumors have disappeared, clinically significant (resulting in clinical deterioration or requiring change of therapy) disease progression beyond 6 months of treatment, per modified World Health Organization (WHO) response criteria (Appendix D), or intolerance of study treatment, whichever occurs first. Due to the mechanism of action, subjects may experience growth in existing tumors or the appearance of new tumors prior to maximal clinical benefit of talimogene laherparepvec. Therefore, dosing should be continued for at least 6 months from the time of initial dose, provided that the subject has no evidence of clinically significant deterioration of health status requiring discontinuation of treatment with talimogene laherparepvec and is able to tolerate the treatment.

The dose, start date, and lot number of talimogene laherparepvec are to be recorded on the electronic case report form (eCRF).

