All other lesions (or sites of disease), including any measurable lesions that were not chosen as index lesions will be identified as nonindex lesions. Nonindex lesions should be recorded and assessed qualitatively over the course of therapy.

Follow-up "Index Lesions":

At each subsequent tumor assessment, the SPD of the index lesions are added together to provide the total tumor burden.

Follow-up "Nonindex Lesions":

Nonindex disease measurements are not required and these lesions should be followed as "present," "absent," or in rare cases "unequivocal progression".

Response Criteria

Evaluation of Objective Response:

The subject response will be assessed based on the response of the index lesions and nonindex lesion, and presence or absence of new lesions. Confirmation of complete or partial response is not required. The overall response is derived from time point response assessments as described in [Table 5](#), [Table 6](#), and [Table 7](#).

Table 5. Definition of Index Lesion Tumor Response Including New Lesions

Complete Response (CR):	Complete disappearance of all index lesions, including any new tumors which might have appeared. Any residual cutaneous or subcutaneous index lesions must be documented by representative biopsy to not contain viable tumor.
Partial Response (PR):	Achieving a 50% or greater reduction in the SPD of the perpendicular diameters of all index lesions at the time of assessment as compared to the sum of the products of the perpendicular diameters of all index lesions at baseline. If any new lesions have appeared, the sum of products of the perpendicular diameters of new measurable lesions must have reduced by 50% or more from when first documented.

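### Appendix D's total tumour burden leaves out new measurable lesions, so the recorded burden can fall while measured tumour is flat or rising

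*Protocol*

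**What the plan says.** Appendix D, under baseline documentation of index lesions, states: "At baseline, up to 10 measurable cutaneous, nodal, or soft tissue lesions will be chosen to measure over the course of therapy". The same paragraph adds: "The distribution of these index lesions should be representative of the subject's overall disease status". Everything else is nonindex: "All other lesions (or sites of disease), including any measurable lesions that were not chosen as index lesions will be identified as nonindex lesions". These are followed qualitatively and need not be measured. The follow-up rule is then: "At each subsequent tumor assessment, the SPD of the index lesions are added together to provide the total tumor burden".

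New lesions are handled elsewhere:

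- Section 6.2.1.1 warns that "subjects may experience growth in existing tumors or the appearance of new tumors prior to maximal clinical benefit of talimogene laherparepvec", and Section 3.1 says much the same.
- Table 5 lets a subject with new measurable lesions be a partial responder only if the summed area of those lesions has at least halved since first documented.
- Under the splitting rule, the largest measurable part of a split index lesion keeps its index status and the other parts are recorded as new lesions.

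Change in tumour burden is a secondary efficacy endpoint in Protocol Section 10.1.1.2. It is also an outcome for the correlations with baseline CD8+ density and with change in CD8+ density. The visible SAP text (Section 11.3) says only that it will be summarised for responders and gives no formula. Parts of SAP Sections 6 and 11.4 are redacted.

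**The concern.** A quantity called total tumour burden should rise when measurable tumour is added. This one cannot, because the set of lesions that count is closed at baseline. The measurements that would correct it are already taken for Table 5, and then dropped from the sum.

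Dosing is meant to continue through early growth and new lesions, so these subjects stay on treatment and under assessment. In them the recorded change may be wrong in size and sometimes in sign. The CD8+ correlations would then relate the biomarker to shrinkage of a baseline subset of lesions rather than to change in the subject's measured disease. Section 2.3 says the study should inform on mechanisms "of systemic action of talimogene laherparepvec on distant metastatic tumors", so the omission is not peripheral to its purpose.

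**Working it through.** **Size of the gap.** Let I0 and It be the index SPD at baseline and at assessment t, and Nt the SPD of new measurable lesions at t. There are no new lesions at baseline, so both versions share the denominator I0.

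- Recorded change = (It - I0)/I0
- Change in all measured tumour = (It + Nt - I0)/I0
- Gap = Nt/I0. The sign reverses when It is below I0 and Nt exceeds I0 - It.

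**Illustrations.** All lesion sizes are assumed; the documents give none.

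| Case | I0 | It | Nt | Recorded | All measured |
|---|---|---|---|---|---|
| New lesion appears (cm²) | 4 | 2 | 3 | (2-4)/4 = -50% | (2+3-4)/4 = +25% |
| 40x20 mm lesion splits into 20x20 and 18x18 (mm²) | 800 | 400 | 324 | -400/800 = -50% | (724-800)/800 = -9.5% |
| New lesions shrink 600 to 300 (mm²) | 1000 | 500 | 300 | -50% | -20% |
| New lesions shrink 2000 to 1000 (mm²) | 1000 | 500 | 1000 | -50% | +50% |

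In the last two rows the new lesions have halved, so Table 5 allows partial response. Limiting the summary to responders therefore does not remove the gap. In the split case, 76 mm² of 800 has gone; the rest of the recorded fall is relabelling.

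**The plan's own index-based figure.** Section 10.2 correlates CD8+ change with the largest index-lesion shrinkage: 55 subjects, null r = 0.30, one-sided 5%, true r = 0.60.

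- Critical r = tanh(atanh(0.30) + 1.645/√52) = 0.491 (stated 0.49)
- Power = Φ((atanh(0.60) - atanh(0.491))·√52) = 0.87 (stated above 80%)

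Both reproduce, so no stated design figure is wrong.

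**Conditional sensitivity.** Suppose r = 0.60 holds for change in all measured tumour, and index-only change correlates ρ with that, so that the observable r is 0.60ρ. The documents do not give ρ.

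| ρ | r | Power |
|---|---|---|
| 1.00 | 0.60 | 87% |
| 0.95 | 0.57 | 79% |
| 0.90 | 0.54 | 68% |
| 0.80 | 0.48 | 46% |

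If CD8+ change in fact tracks the index lesions, there is no loss. The table shows what could be at stake and does not estimate it.

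**Objective response, checked separately.** Appendix D states: "The subject response will be assessed based on the response of the index lesions and nonindex lesion, and presence or absence of new lesions". In Table 5, complete response requires new tumours to have gone, partial response requires new measurable lesions to have halved, and an unequivocal new tumour is progression. In Table 7, nonindex persistence lowers an index complete response to partial, and nonindex progression overrides an index response.

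**The case against.** The strongest reply is that an index-lesion measure is a declared choice. Sections 10.2, 10.4 and 10.4.2 all name the largest index-lesion decrease as the variable to be correlated with biomarker change, and no formal hypothesis is tested. That stands for the one Pearson analysis. It does not define the separate tumour-burden endpoint or the correlations with baseline CD8+ density, for which the only visible definition is the Appendix D sum.

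The SAP redactions could hide a fuller derivation. That also stands, and it makes the point conditional on the visible text.

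A reader might infer that ORR is distorted too, because new and visceral lesions count as zero. The documents do not support this: Tables 5 to 7 bring both into response. Two narrower features remain. New lesions are judged against their own first size, and nonindex growth counts only when unequivocal. Both are stated parts of the modified criteria, not omissions.

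A reader might also want visceral and lung lesions made index lesions. On the plain reading they are outside the sum, which sits badly with the call for a representative set. But changing this would alter partial response and progression, and so the response variable in the primary endpoint. Cutaneous and nodal lesions can themselves be distant disease (stage M1a, Section 2.1), and Section 6.2.1.1 keeps one lesion uninjected until week 6 in subjects with at least two, so index lesions can still show a systemic effect.

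Finally, a reader might attach a number of affected subjects. The documents give neither the stage mix nor the share with new lesions, so any count would be an assumption.

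**Conclusion.** The point holds for the tumour-burden endpoint and its CD8+ correlations. Followed as written, the sum omits new measurable lesions and overstates shrinkage by Nt/I0: 75 percentage points in the first illustration and 40.5 in the split-lesion case, both with assumed sizes. The sign can reverse. The overall effect on the trial's results cannot be computed from the documents.

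The conclusion rests on the visible Appendix D rule being the one that is programmed. It does not extend to ORR or to the stated power figures. The tension between the index-lesion site list and the representativeness requirement is a separate matter of wording and reporting.

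**What to change.** 1. In Appendix D and the SAP, define tumour burden at each assessment as the SPD of index lesions plus the SPD of all new measurable lesions, including measurable fragments of split lesions. Use it for the tumour-burden endpoint and the CD8+ correlations that have burden as outcome.
2. Keep the index-only sum, including the planned analysis of largest index-lesion decrease, as a sensitivity analysis labelled *index lesion burden*. State in the SAP which version feeds each objective.
3. Reconcile the cutaneous, nodal and soft tissue list with the representativeness sentence, and report that visceral lesions are not in the sum. Leave the response criteria unchanged.
4. If redacted SAP text already defines burden as in item 1, align Appendix D with it.

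The cost is wording and programming; no further scans or measurements are needed, because Table 5 already requires the new-lesion areas. The downside is that reductions may look smaller and be less comparable with index-only results elsewhere, which the sensitivity analysis partly offsets.
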